6.8.5 Urinalysis

Urinalysis data will be summarised and listed.

Potentially clinically significant values will be defined as displayed in [Table 5](#).

Table 5: Potentially clinically significant urinalysis values

Protocol lab parameter (ACM lab parameter)	SI unit	PCS low	PCS high
Erythrocytes	/HPF	N/A	> 3, >10, >25, >30
Leucocytes	/HPF	N/A	> 10
Casts (hyaline casts)	/LPF	N/A	> 2
Casts (WBC casts)	/LPF	N/A	Few, moderate, many
Casts (RBC casts)	/LPF	N/A	Few, moderate, many
Casts (waxy casts)	/LPF	N/A	Few, moderate, many
Casts (granular casts)	/LPF	N/A	Few, moderate, many

Abbreviations: ACM = ACM Global Laboratories; HPF = high power field; LPF = low power field; N/A = not applicable; PCS = potentially clinically significant; RBC = red blood cells; ULN = upper limit of normal (i.e., upper limit of normal reference range); WBC = white blood cells.

6.8.6 Pharmacokinetics and anti-drug antibodies

Pharmacokinetics and ADA data will be summarised and listed.

The ADA status will be categorised as follows:

- Positive
 1. Pre-existing: ADA-positive at baseline, no post-baseline ADA response \geq 4-fold over baseline titre level, and at least 1 non-missing post-baseline ADA assessment.
 2. Treatment-boosted: ADA-positive at baseline and at least 1 post-baseline ADA response \geq 4-fold over baseline titre level.
 3. Treatment-emergent: ADA negative or missing at baseline and at least 1 positive post-baseline ADA response.
- Negative
 1. ADA negative or missing at baseline, all post-baseline ADA assessments negative.
- No post-baseline ADA assessment.

6.9 General principles

6.9.1 Baseline value

Unless otherwise specified, the baseline value is defined as the latest pre-dose assessment.

6.9.2 Definition of trial periods and date of permanent discontinuation of IMP

Date of permanent discontinuation of IMP (tralokinumab/placebo)

Defined for subjects who have a reason for permanent discontinuation of IMP (tralokinumab/placebo) recorded.

Defined as the latest of date of early termination visit (if existing) or date of onset of latest AE leading to withdrawal of trial product, otherwise date of the last visit, excluding safety follow-up and nominal Week 16 visits.

Exposure start

Date and time of first dose.

Exposure end

Date of Week 16 visit (if existing) at time 23:59:00, otherwise date of permanent discontinuation of IMP (tralokinumab/placebo) at time 23:59:00.

Trial periods

The time from exposure start to exposure end will be assigned to the treatment period and remaining time after exposure end will be assigned to the safety follow-up period as shown in [Table 6](#) (ADaM variable APHASE). The ADaM variable APERIODC will indicate the latest treatment at any given time point, thus not including a follow-up period ([Table 7](#)).

Table 6: Start and end time of trial periods (ADaM variable APHASE)

APHASE	Start of period	End of period (only if start date exists)
Treatment period	Exposure start	Exposure end
Safety follow-up period ¹	Exposure end (plus 1 second)	Date of safety follow-up visit (if existing) at time 23:59:00 else Date of last contact at time 23:59:00

1) Only applicable if date of last contact is not equal to date of exposure end.

Table 7: Start and end time of trial periods (ADaM variable APERIODC)

APERIODC	Start of period	End of period (only if start date exists)
-----------------	------------------------	--

Treatment period	Exposure start	Date of last contact at time 23:59:00
------------------	----------------	---------------------------------------

6.9.3 Incomplete recordings

Adverse events

If the AE start day is missing, but AE start month and year are not missing, the following rules apply:

- If the year and month of the AE start is before the year and month of the exposure start, or if the AE end date is complete and before the exposure start, the AE will not be considered treatment-emergent.
- If the year and month of the AE start is the same as the year and month of the exposure start, the AE will be considered treatment-emergent and assigned to the treatment period, unless the AE has a complete end date which is before exposure start.
- If the year and month of the AE start is after the year and month of exposure start, it will be assumed that the AE started on the first day of the month and the AE will be assigned to the treatment or safety follow-up period accordingly.

If the AE start month is missing, but AE start year is not missing, the following rules apply:

- If the year of the AE start is before the year of the exposure start, or if the AE end month is not missing and before the month of the exposure start, or if the AE has a complete end date which is before the exposure start date, the AE will not be considered treatment-emergent.
- If the year of the AE start is the same as the year of the exposure start, the AE will be considered treatment-emergent and assigned to the treatment period, unless the AE end month is not missing and before the month of the exposure start or the AE has a complete end date which is before the exposure start date.
- If the year of the AE start is after the year of exposure start, it will be assumed that the AE started on the 01 January and the AE will be assigned to the treatment or safety follow-up period accordingly.

Concomitant medication

For incomplete start dates of concomitant medication, the following rules apply:

- If a medication start day is missing, but start month and year are not missing, it will be assumed that the start day is the first day of the month. If the medication start day and

month are missing, but start year is not missing, it will be assumed that the start day is 01 January. If the medication start day, month, and year are missing, it will be assumed that the medication was started before trial start, and the date will appear as missing in the data.

For incomplete end dates of concomitant medication, the following rules apply:

- If a medication end day is missing, but end month and year are not missing, it will be assumed that the end day is the last day of the month. If the medication end day and month are missing, but end year is not missing, it will be assumed that the end day was 31 December. If the medication end day, month, and year are missing, it will be assumed that the medication was ongoing at the end of the trial, and the date will appear as missing in the data.

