## 7 Trial design

### 7.1 Overall trial design

#### Overview

This is a randomised, double-blinded, placebo-controlled, phase 2 trial in adult subjects with moderate-to-severe AD. The primary objective of the trial is to demonstrate non-inferiority of tralokinumab versus placebo with respect to immune response to concomitantly administered Tdap and meningococcal vaccines. The trial will evaluate the percentage of subjects achieving a positive anti-tetanus response at Week 16 and a positive meningococcal response at Week 16.

The trial will consist of a screening period of 2 to 6 weeks (Weeks -6/-2 to 0), a treatment period of 16 weeks (Weeks 0 to 16) and a 14-week off-treatment follow-up period for the assessment of safety (Weeks 16 to 30). The primary endpoints will be assessed at Week 16, and the final safety assessment will be conducted at Week 30 (end-of-trial visit). Eligible subjects may transfer to the open-label ECZTEND trial (LP0162-1337) at Week 16 or later. An overview of the different parts of the trial is provided in [Panel 1](#).

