#### **14.3.8.1 Adverse events**

AEs will be coded during the course of the trial according to Medical Dictionary for Regulatory Activities (MedDRA). AEs will be presented by preferred terms and primary system organ class (SOC).

Treatment-emergent AEs will be summarised, however, all AEs recorded during the course of the trial will be included in the subject data listings. An event will be considered treatment-emergent if started after the first use of IMP or if started before the first use of IMP (applicable if subject had a wash-out) and worsened in severity thereafter. The tabulations described in the following will only include the treatment-emergent events. In each of the tabulations, AEs will be defined by MedDRA preferred terms within primary SOC.

An overall summary of the number of treatment-emergent AEs, number (percentage) of subjects with any treatment-emergent AEs, SAEs, deaths, premature discontinuations from the trial due to AEs, treatment-related AEs and severe AEs will be presented.

The number of AEs and the number of subjects experiencing each type of AE will be tabulated by treatment group. The percentage of subjects with AEs will be compared between treatment groups by a chi-square test or Fisher's exact test (if expected cell count < 5).

The severity for each type of AE will be tabulated by treatment group.

The causal relationship to IMP (tralokinumab/placebo) for each type of AE will be tabulated by treatment group. Related AEs are defined as AEs for which the investigator has not described the causal relationship to IMP as 'not related'. The number of related AEs and the number of subjects experiencing each type of related AE will be tabulated. The percentage of subjects with related AEs will be compared between treatment groups by a chi-square test or Fisher's exact test (if expected cell count <5).

The causal relationship to IMP (each vaccine) for each type of AE will be tabulated by treatment group. Related AEs are defined as AEs for which the investigator has not described the causal relationship to IMP as 'not related'. The number of related AEs and the number of subjects experiencing each type of related AE will be tabulated. The percentage of subjects with related AEs will be compared between treatment groups by a chi-square test or Fisher's exact test (if expected cell count <5).

SAEs and AESIs will be evaluated separately and a narrative for each will be given. AEs leading to withdrawal from trial will be listed.

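### SAP 6.9.3: when an AE's start month is missing, its end month is compared with the month of first dose without naming the year, so read literally an AE ending in the next calendar year is not treatment-emergent

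*SAP*

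**What the plan says.** SAP 6.9.3, under adverse events, gives two sets of three bullets.

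- **Start day missing.** Year and month are handled as a pair throughout, beginning "If the year and month of the AE start is before the year and month of the exposure start".
- **Start month missing, start year known.**
  - Bullet 1 makes the event not treatment-emergent if any one of three conditions holds: the start year is earlier than the year of first dose; a fully recorded end date falls earlier than first dose; "or if the AE end month is not missing and before the month of the exposure start".
  - Bullet 2 covers a start in the same year as first dose. The default is treatment-emergent, in the treatment period, "unless the AE end month is not missing and before the month of the exposure start" or a complete end date shows that the event was over before first dose.
  - Bullet 3 opens "If the year of the AE start is after the year of exposure start". It assumes onset on 1 January and allocates the event to treatment or safety follow-up.

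SAP 6.9.2 defines exposure start as the date and time of first dose. Protocol 14.3.8.1 states: "The tabulations described in the following will only include the treatment-emergent events". It also states that "all AEs recorded during the course of the trial will be included in the subject data listings".

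**The concern.** The end-month test in bullets 1 and 2 names a month and no year. The rule just above it, for the same purpose, names both. A programmer who implements the text as it stands has grounds to compare month numbers, and that goes wrong whenever first dose and AE end lie in different calendar years. The complete-end-date condition does not repair this: it is joined by an *or*, so a full end date in the following year cannot override the month test.

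An event misclassified in this way disappears from the AE tabulations, and the number of AEs is an additional secondary endpoint (Protocol section 6). The error can only remove events:

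- If the AE start year equals the year of first dose, the end year cannot be earlier, so the month test never wrongly keeps an event.
- If the start year is earlier, bullet 1 excludes the event anyway.
- If the start year is later, the month test in bullet 1 can only work against bullet 3.

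For safety tables, losing events is the non-conservative direction.

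**Working it through.** The plan gives no figure to reproduce here. The check applies the rule both ways.

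**Inputs.** The wording is that of SAP 6.9.3. Observation after first dose is "a treatment period of 16 weeks (Weeks 0 to 16) and a 14-week off-treatment follow-up period" (Protocol 7.1), so 16 + 14 = 30 weeks = 210 days. The years below are illustrative.

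**Two versions of the test.**

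- Month only: not treatment-emergent if end month < first-dose month.
- Year and month: not treatment-emergent if (end year, end month) is earlier than (first-dose year, first-dose month).

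**Worked cases, first dose 15 October 2018.**

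| AE start | AE end | Month only | Year and month |
|---|---|---|---|
| 2018 | Sep 2018 | 9 < 10: not treatment-emergent | not treatment-emergent |
| 2018 | Nov 2018 | 11 > 10: treatment-emergent | treatment-emergent |
| 2018 | Feb 2019 | 2 < 10: **not treatment-emergent** | treatment-emergent |
| 2019 | Feb 2019 | bullet 1: **not treatment-emergent**; bullet 3: assigned to a period | bullet 3 only: assigned to a period |

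In the third row the month test overrides bullet 2's default for an event that did not end before first dose. In the fourth row the event must have begun after first dose. Bullet 3 places its onset at 1 January 2019, which is day 16 + 30 + 31 + 1 = 78. That is inside the 112-day treatment period if the subject completes it. Bullet 1 says the opposite.

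**All combinations.** Take every first-dose day of a 365-day year and every AE end from day 0 to day 210: 365 × 211 = 77,015 combinations.

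- First doses from 5 June (1 next-year end day) to 31 December (210 next-year end days) can have an end in the following year: 1 + 2 + … + 210 = 210 × 211 / 2 = 22,155 combinations.
- The remaining 77,015 − 22,155 = 54,860 end in the year of first dose.
- With AE start in the year of first dose, the two versions disagree in 22,155 of 22,155 next-year combinations and in 0 of 54,860 same-year combinations.
- With AE start in the following year, bullet 1 conflicts with bullet 3 in 22,155 of 22,155.

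**Why it is all or nothing.** To end in the next year with a month number at least as large as that of first dose, an event must end at least 335 days later (for example 31 October 2018 to 1 October 2019: 365 − 30 = 335). Observation is 210 days, so within it the next-year end month is always the smaller number.

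**The case against.** The best reply is that the phrase describes time order, not month numbers. Exposure start is a single dated moment, so its month is a particular month of a particular year, and February 2019 is not before October 2018. On that reading the three bullets agree with each other and with the rule above them. A reading that sets bullets 1 and 3 against each other is unlikely to be the one intended. This largely stands as a statement of intent. It does not make the text safe: no other section supplies the year, the neighbouring rule shows that the authors name the year when they mean it, and a programming specification should not rest on inference.

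The safeguards also count. AEs are asked about at every visit (Protocol 13.2), so a missing start month should be rare. Discrepant data are queried (Protocol Appendix 3D). The eCRF records whether the AE began before first dose (Protocol 13.3), although the SAP rule does not use that item. All AEs are listed, and serious AEs and AEs of special interest receive narratives (Protocol 14.3.8.1). The rule is the same in both arms.

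A reader might infer more than the documents support:

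- **That any AE crossing the year end is lost.** Only AEs with start month missing, start year known and end month recorded are exposed. AEs lacking only the start day, and ongoing AEs with no end month, are not.
- **That long-lasting events are the ones removed.** With the start month unknown, so is the duration. An event from late December to early January is caught as well.
- **That a large share of AEs is affected.** If first doses were spread evenly over the year, 112/365 = 31% of 16-week treatment periods and 210/365 = 58% of 30-week windows would cross 31 December. These are shares of observation windows, not of AEs. Even spread is not stated, and transfer to the extension trial from Week 16 shortens some windows.
- **That every removed event began on treatment.** An end after first dose does not prove onset or worsening after it. In the same-year case the event belongs in the tables because bullet 2's default puts it there.

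**Conclusion.** Wrong as written, minor. For AEs with the start month missing, the start year known and the end month recorded, the literal test always excludes an event that ends, within the 30-week observation, in the calendar year after first dose. That overrides bullet 2's default, and for a start year after first dose it contradicts bullet 3. The conclusion rests on the literal month comparison, which the text permits and nothing in it corrects, although the intended meaning was probably year and month. Such events would be missing from the treatment-emergent tables only. The number of events is probably small or zero; the documents give no frequency, so it cannot be estimated.

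**What to change.** In both bullets, word the condition as: *the AE end year and month are not missing and are before the year and month of the exposure start*. This changes no same-year case and removes the conflict between bullets 1 and 3.

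Then check the derivation against the eCRF item on onset before first dose: list any AE with a missing start month that is classed as not treatment-emergent but recorded as not having started before first dose.

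The cost is two phrases in the SAP and, if the derivation is already programmed, a review of that step. No data collection or main analysis changes.

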The criteria related to systemic rescue medication in the definition of the per protocol analysis set have been updated relative to the protocol text to include, not only those for the AD indication but all systemic immunosuppressive treatments irrespectively of indication. The referred criteria for excluding patients consequently become:

- Initiated systemic immunosuppressive treatment prior to Week 10 and who are still treated with or exposed to the given treatment at Week 10 (that is, Week 10 [visit 8] occurs within 5 half-lives after the last dose of the given systemic immunosuppressive medication).
- Initiated systemic immunosuppressive treatment at any time point from Week 10 to Week 16.

The rationale for excluding these subjects is to ensure that subjects were not immunosuppressed by these treatments when the vaccinations were administered, as this might impact the response to the vaccination, and thereby the primary endpoints. This is independent of the indication for the immunosuppressive treatments and should therefore include all subjects treated with systemic immunosuppressants, irrespectively of the indication.

In addition to the criteria specified in the protocol, subjects with Week 16 visit occurring ≥ 56 days after the Week 12 visit, are not included in per protocol analysis set due to a too long interval between administration of the vaccine and measurement of the vaccine response, since this would induce a risk of a perished vaccine response.

Systemic immunosuppressive treatment definition

ATC2 code H02 or L04 will be used to identify administered systemic immunosuppressive treatments. [Table 1](#) below presents the medications that as minimum will be identified in the trial (as being systemic immunosuppressive) along with the half-lives applied to evaluate the PP exclusion criteria.

Medications administered in the screening period will be included in the search to ensure that all administered medications that could potentially be immunosuppressive at time of vaccination will be covered. Different routes of administration can be used for the medications, which will result in different half-lives.

Table 1: Systemic immunosuppressive treatments and applied halflives

ATC 4	ATC 4 TERM	Standardized Medication Name	Route of Administration	Halflife		
				Hours	Weeks	5 x t _{1/2} ¹
H02AB	GLUCOCORTICOIDS	DEXAMETHASONE	ORAL	7.2	0.0	0.2

H02AB	GLUCOCORTICOIDS	DEXAMETHASONE SODIUM PHOSPHATE	INTRAVENOUS	24	0.1	0.7

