6.3 Rescue medication

Rescue medication is defined by the following algorithm: Concomitant medications with Dermatitis atopic or Dermatitis infected as the preferred term for the indication and either ATC2 code H02 or D07, or ATC4 code D11AH, or preferred name Methotrexate, Ciclosporin, Azathioprine, Mycophenolate-mofetil, Mycophenolate-sodium, Mycophenolate-acid, or Dupilumab.

According to the protocol, investigators should make every attempt to conduct efficacy and safety assessments immediately before administering any rescue treatment. Therefore, if rescue medication has start date the same day as an efficacy assessment, then the assumption will be that the assessment is not influenced by the rescue medication.

The table of rescue medication will include medications taken after the first dose and before the Week 16 visit (or before day $7 \times 16 = 112$ after first dose, in case the Week 16 visit did not take place).

Rescue medication will be summarised for the treatment period. In addition, a summary table of rescue medication by type (topical and systemic) and by overall group (corticosteroids, immunosuppressants, and other) will be made.

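### The partial-date rules for concomitant medication (SAP 6.9.3) lack the first-dose check given to adverse events and could misclassify efficacy rescue status and, less often, per-protocol membership

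*SAP*

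**What the plan says.** SAP 6.9.3 pushes partial medication dates outward in both directions. For starts:
- day missing: "it will be assumed that the start day is the first day of the month";
- day and month missing: 01 January;
- whole date missing: "it will be assumed that the medication was started before trial start".

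For ends:
- day missing: "it will be assumed that the end day is the last day of the month";
- day and month missing: "it will be assumed that the end day was 31 December";
- whole date missing: "it will be assumed that the medication was ongoing at the end of the trial".

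None of these is compared with first dose. The adverse event rule in the same section is: when the start falls in the month of exposure start, "the AE will be considered treatment-emergent and assigned to the treatment period, unless the AE has a complete end date" that precedes exposure start.

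These dates matter in two places.
- **Rescue.** SAP 6.3 identifies rescue by indication and drug code, and "The table of rescue medication will include medications taken after the first dose and before the Week 16 visit". Protocol 14.3.6.1 names the intercurrent event as the initiation of rescue, and 14.3.6.3 and 14.3.7 discard data after initiation. The primary analysis in 14.3.6.2 makes subjects who received rescue before Week 16 non-responders.
- **Per-protocol set.** SAP 5 excludes subjects who started a systemic immunosuppressant before Week 10 and are still treated or exposed at Week 10 (within 5 half-lives), and those who start one from Week 10 to Week 16. "Medications administered in the screening period will be included in the search", and so are drugs that required wash-out.

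Protocol 9.6 records medication from 3 months before screening, so washed-out drugs are in the database.

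**The concern.** Rescue status decides response for IGA 0/1 and EASI75, and the date of rescue decides which data enter the hypothetical-estimand and repeated-measures analyses. Neither document says outright whether the start date or overlap with treatment makes a medication rescue, and each reading has its own error.

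- **Start date decides.** Rescue truly begun after first dose in that month, with the day missing, is dated to the first of the month. It then looks like pre-trial medication. The subject keeps any Week 16 response, and data collected under rescue stay in analyses meant to exclude them.
- **Overlap decides.** That subject still counts as rescued, but initiation now precedes all post-baseline visits, so all post-baseline data are dropped. SAP 6.7 then enters a change of 0 at the first post-baseline assessment. In addition, a topical steroid stopped for wash-out, with a partial stop date, can be extended into the treatment period and make the subject a false non-responder.

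Separately, an end date imputed too late can show a washed-out systemic immunosuppressant as active at Week 10 and remove the subject from the primary non-inferiority set.

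**Working it through.** **Plan's own figures (Protocol 14.1).** 80 per arm in the per-protocol set, 80% response in both arms, margin 25 points, one-sided 2.5%: SE = √(2 × 0.8 × 0.2 / 80) = 0.0632; 0.25/0.0632 − 1.96 = 1.99; power 97.7% (plan: 98%). With 100 per arm, IGA 0/1 at 30% v 10% gives 94.8% and EASI75 at 40% v 15% gives 98.1%. All four, independent: 0.977² × 0.948 × 0.981 = 88.8% (plan: about 89%). Both figures reproduce.

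**Assumption for the date checks.** First-dose dates are spread evenly over the calendar year; mean month length L = 365/12 = 30.4 days. Every result below is conditional on the date being partial.

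**Start day missing.** The imputed start is on or before first dose exactly when the true start (Day u) lies in the calendar month of first dose, with probability about (L − u)/L for u < L and 0 beyond.
- Days 1-14: 1 − 7.5/30.4 = 75%.
- Days 1-30: 1 − 15.5/30.4 = 49%.
- Days 1-111: (30 − 465/30.4)/111 = 13%.

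Applying the rule to every date in a year gives the same values. Counting only imputed starts strictly before first dose gives 72%, 46% and 12%. With the month also missing, 85% of starts on Days 1-111 go on or before first dose.

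**End day missing, topical steroid (overlap reading only).** Exclusion criterion 9 requires a 2-week wash-out. For a stop g days before first dose, the imputed end is on or after first dose with probability about (L − g)/L.
- g = 14: 54% (51% strictly after).
- g = 21: 31% (28% strictly after).
- Stops spread evenly over 14-42 days before: 16%.

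**Per-protocol set, systemic drug stopped 28 days before first dose (criterion 8).** Week 10 is Day 70.
- Only the end day missing: the imputed end is at most Day +2. Adding SAP Table 1's 5 × half-life for oral prednisone (0.1 weeks), methotrexate (0.4) or IV dexamethasone (0.7 weeks = 4.9 days) reaches about Day 7 at most. None is wrongly excluded.
- Drugs with a 10.0-week value (IM triamcinolone, SC dexamethasone): true exposure ends on Day −28 + 70 = Day 42. It is imputed to Days 70-72 when the stop is in the month of first dose: 7 × 3 dates in 31-day months plus 4 × 2 in 30-day months = 29 of 365 = 8%.
- End month missing: 31 December of the stop year reaches Day 70 when first dose falls from 29 January to 22 October, 267/365 = 73%.
- Whole end date missing: assumed ongoing, so always active at Week 10.

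A shifted start does not change per-protocol status. Of true starts in Weeks 10-16 with the day missing, 34% move before Week 10, but the course still runs at or after Week 10, so the first criterion catches it.

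**Size on the endpoints (illustration; the true share is not in the documents).** One subject is 1 point of an arm of 100. Suppose a share f in both arms become false non-responders and the same share is lost from the per-protocol set.

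| f | Non-inferiority power | All four hypotheses |
|---|---|---|
| 0 | 97.7% | 88.8% |
| 1% | 97.6% | 88.2% |
| 2% | 97.5% | 87.6% |
| 5% | 97.1% | 85.7% |

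If instead missed rescue adds 1 or 2 points to the placebo IGA 0/1 rate alone, IGA power is 92.0% or 88.4%.

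**The case against.** The strongest case on the other side has four parts.

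1. **The documents lean towards the start date.** The protocol names initiation as the event, and SAP 6.3 uses the rescue start date for its same-day rule. The phrase about medication taken after first dose governs a table. On that reading, starts only move earlier, so a pre-trial drug can never become on-trial rescue. This stands, and it confines the washed-out-steroid error to the overlap reading. It does not remove the lost-rescue error, which arises on the favoured reading. Nor is the reading settled: Protocol 14.3.6.2 also speaks of rescue received, and SAP 6.1 uses overlap for baseline medication.

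2. **A missing start day should be rare for on-trial rescue.** Rescue is at the investigator's discretion, visits are every 2 weeks, start and stop dates plus an ongoing flag are collected (Protocol 9.6), and discrepant data are queried (Appendix 3D). This stands as a reason to expect few cases. The 75% and 49% also apply only to early rescue; over the treatment period the figure is 13%.

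3. **The per-protocol effect is narrow.** It needs a missing end month or whole end date, or a 10-week drug. The primary endpoints are also analysed on the full analysis set, and non-inferiority power barely moves. This stands.

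4. **Capping imputed end dates at the wash-out limit would presume that wash-out succeeded.** The per-protocol search deliberately includes drugs that required wash-out, and a cap would blunt the check for failed wash-out. This stands, so no cap is proposed.

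**Conclusion.** The gap is real: medication lacks the first-dose check that adverse events have, and the definition of rescue that would decide the consequence is not stated. Efficacy rescue status could be wrong under either reading. The percentages rest on evenly spread first-dose dates and on the date being partial. Without the share of partial dates no absolute effect can be computed; it is probably small.

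Three stronger conclusions might be inferred, and the documents do not support them.
- That the rules both create false rescue and lose real rescue: these errors belong to different readings, and false rescue comes from the end-date rules, not the start-date rule.
- That subjects are misclassified, rather than could be: complete dates are to be collected.
- That the primary result is undermined: rescue does not define vaccine response, and the per-protocol error is wrongful exclusion only.

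This is an inexpensive correction worth making before unblinding, not a threat to the trial's main conclusion.

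**What to change.** 1. In SAP 6.9.3, for medication meeting the rescue algorithm (6.3) or the systemic immunosuppressant search (5): treat a partial start whose known part matches the month, or the year, of first dose as after first dose, unless the end date shows that it ended before first dose. This mirrors the adverse event rule.
2. In SAP 6.3, state that rescue for the endpoints means medication started or restarted after first dose. A pre-trial drug is then not made rescue by an imputed end date alone.
3. Before unblinding, list every rescue or per-protocol decision that rests on an imputed or wholly missing date, and settle each one blinded against the source record and the wash-out documentation. This covers the end-date cases without an automatic cap. It also covers the side effect of item 1, where a pre-trial drug with only the year known for both dates would be called on-trial.

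The cost is a few lines of SAP text, a small change to derivation code and one blinded listing. No new data are needed.
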